Aim 1: We will randomize **304 participants**; 76 to CM alone, 76 to CM+NH, 76 to CM+ ER, and 76 to CM+NH+ER. Based on the previous work with the SIQ, we believe a 25% reduction among individuals with a score of 30 or greater would represent clinically significant change in suicide ideation.[5] Using pilot data of NH among the WMAT, an average baseline score of 45 could be expected on the SIQ.[5] A clinically significant reduction translates into a large Cohen's D effect size (>0.8). However, we want the power to observe the more moderate effect expected to result from comparing the sequencing of the interventions (NH+ER vs. NH+CM vs. CM+ER vs. CM alone). Using an adjusted alpha to account for multiple comparisons of 0.013, and a correlation of 0.2 among repeated measures, with four groups (NH+ER vs. NH+CM vs. CM+ER vs. CM alone), $n=58$ people per group ($n=116$ randomized at each randomization time-point) would provide 80% power to detect a small to moderate effect (Cohen's $F=0.2$). Adjusting these estimates for 30% attrition would result in $n=76$ per each of the four groups ($n=152$ per arm) for a total sample size of $N=304$.

Please note for our ***the Opioid Data Collection Sub-Study***: We will use a mixed methods approach to examine opioid use among our SMART trial participants through addition of a quantitative opioid related measure and qualitative interviews ($N=30$) with a subset of those who endorse recent or current use.

For the economic evaluation supplement: We will use the same sample of participants as Aim 1. We are not drawing statistical inferences about cost estimates so there is no sample size requirement. Instead, we are reporting on the health care services utilization and costs incurred by study participants before, during and after the intervention. To administer a time use survey and conduct in-person interviews we will use all HUB program case managers (five or more) and healthcare providers (three or more).

For the diversity supplement: We will use a sub-sample of $n=239$ WMAT participants enrolled in the parent trial. This sample size is based on the estimated enrollment rates during the Diversity Supplement study period.

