Aim 3: Study participants will be 25-50 key stakeholders including youth, caregivers, program providers, community members, tribal leaders, and other researchers across the Hub, including satellite partners. Sample size for Aim 3 is based on qualitative research theory on saturation, a point after which common themes and information from respondents tend to converge. Quantitative data collected is exploratory in nature and will be used to help inform future implementation and scale-up of the programs.

Please note for our ***the Opioid Data Collection Sub-Study***: Key stakeholders will only be asked about opioid use generally in relation to the community, not their personal use. However, we are aware that personal use may still be disclosed. We will use the same referral and follow-up procedures for these participants as those in our SMART trial. We estimate 25 participants based on the number of Hubs sites and advisory board members.

IV. Participants:

Describe the study participants and the population from which they will be drawn. Specify the inclusion and exclusion criteria. If you plan to include children, note their ages and whether you will include children in foster care.

Note if the participants are particularly vulnerable in terms of cognitive limitations, education, legal migration status, incarceration, poverty, or some combination of factors.

Aim 1: Study participants will be self-identified Native Americans who are between the ages of 10 and 29 years old and reside on or near the Fort Apache Indian Reservation and are identified in the existing surveillance and case-management (CM) system as having recently had a validated suicide attempt, ideation, or binge substance use episode and recent ideation. The majority of these tribal populations lives below the federal poverty line. The economic evaluation supplement does not involve any contact with the study participants.

A. Inclusion Criteria:

- Native American youth ages 10 to 29 years old.
- Reside on or near the Fort Apache Indian Reservation.
- Parent/guardian consent for youth under 18 years old.
- Suicide ideation, binge substance use with recent (i.e. within the last 3 months) suicide ideation, or suicide attempt in the past 30 days as identified and verified by the surveillance system OR release from inpatient care related to suicide ideation or attempt within past 30 days

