Terms and Definitions: Definitions for reportable behaviors are modeled on the Columbia Classification Algorithm for Suicide Assessment (C- CASA).[11] **Suicide attempt:** intentional self-injury with intent to die.

(Aborted and interrupted suicide attempts are included as part of this category). **Suicidal ideation:** thoughts to take one's own life with or without preparatory action. **Binge substance use with recent ideation**, defined by Apache stakeholders, as consuming substances with the intention of modifying consciousness and resulting in being found unresponsive or requiring ED treatment and answering positively to a 1-item screening question on the assessment indicating suicide ideation within the past three months.

B. Exclusion Criteria:

- Factors identified at baseline that preclude full participation, including: unstable and severe medical, psychiatric or drug use problem that necessitates inpatient treatment; acute suicidal or homicidal ideation requiring immediate intervention; recent, severe stressful life events such as physical or sexual abuse, or violent crime victimization that requires specific and high intensity interventions or out of home placement. Participants must speak English and not be severely visually impaired. Ambiguous cases will be reviewed by one of the co-PIs before being deemed eligible for recruitment.

Aim 3: Study participants will be 25-50 key stakeholders including youth, caregivers, program providers, community members, tribal leaders, and other researchers across the Hub, including satellite partners. Please note for our opioid supplement: key stakeholders will only be asked about opioid use generally in relation to the community, not their personal use. However, we are aware that personal use may still be disclosed. We will use the same referral and follow-up procedures for these participants as those in our SMART trial.

C. Inclusion Criteria:

- Youth over the age of 16 with parental consent and youth assent or adults over the age of 18 with their consent.
- A person with an interest or concern related to youth suicide among AI populations.

D. Exclusion Criteria:

Factors identified at baseline that preclude full participation including: being under the influence of a substance; active psychosis or mania; any other condition that makes an individual lack capacity to give consent. Children who are a ward of the court/no guardian will not be included.

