Aim 1: The surveillance system will be used to identify youth who have a validated suicide attempt, ideation, or binge substance use episode with recent suicide ideation in the past 30 days or who have a recent event that resulted in in-patient hospitalization/treatment. Those potential participants who have been sent to in-patient care will continue to be eligible to enroll in this study for 30 days after their return from treatment. Please note the opioid related questions added to the SMART trial battery will identify those who have endorsed current or recent opioid use, related to our Opioid Data Collection Sub-Study Aims. Surveillance System Staff will confirm the episode with the youth (i.e. that the reported event happened), then a Research Program Assistant conduct the recruitment process including screening for inclusion and exclusion criteria, using the uniform recruitment script.

Aim 3: Project Leads at each Southwest Hub site will identify stakeholders who may be eligible to participate.

d. Whether you will obtain a signature from the participant or will use an oral consent process:

Aim 1 & 3: We will obtain a signed consent form.

e. Whether you will obtain a legally authorized representative's signature for adults lacking capacity:

Aim 1 & 3: We will not obtain a legally authorized representative's signature for adults lacking capacity. These individuals will be excluded from the study.

f. If children are included in the study, if and how you will obtain assent from them:

Aim 1 & 3: Assent will be obtained through a separate form, after parental consent is obtained. The study will be explained to the child in simple terms and Research Program Assistants will ask prospective youth participants if they fully understand the consent process/forms.

g. If children are included in the study, how you will obtain permission for them to participate from their parent, legal guardian, or other legal authority (if child is in foster care or under government supervision):

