After 30 days from CM3, all youth will be visited by Research Program Assistants and complete a fourth assessment (CM4). The 30-day time frame between CM3 and CM4 will allow ample time to complete the ER intervention with participants and assess any changes in resilience across study groups. To track long-term outcomes, all youth will complete a final assessment 3 month later (CM5: 6 months post-enrollment). All youth will be followed to the end of the study period (up to 4.75 years from the first participant’s enrollment) for any subsequent suicide events using the Apache surveillance system. If necessary, assessments may be conducted over the phone for participants who start in the study but are located elsewhere during an assessment timepoint.

As part of the economic evaluation supplement, our staff will be asked to fill out time logs listing how they spent time the preceding day. This will not affect the study participants in any way.

Aim 3: STUDY PROCEDURE

If stakeholders provide informed consent, they will be interviewed by Drs. [name] or [name] using a semi-structured guide to gather their views on the Southwest Hub’s key intervention components (Surveillance/Case Management, New Hope and Elders’ Resilience Interventions). They will also be asked to participate in a 2x annually administered online survey to better understand how capacity for sustainability changes over time. If they consent to the online survey, the Program Sustainability Assessment Tool (PSAT) will be administered via email to participants every six months.

2. Describe the number and type of study visits and/or contacts between the study team and the participant, how long they will last, and where/how they will take place.

Aim 1: Five study visits will take place over the course of 6 months. All study visits will take place in the participants' home or a private location.

CM1: Recruitment, consent, randomization, baseline assessment: 2 hours

Intervention Group: NH: 2-4 hours

CM2: Assessment: 1 hour

CM3: Assessment and randomization: 1 hour

Intervention Group: EC: 2-4 hours

CM4: Assessment: 1 hour

CM5: Assessment: 1 hour

Opioid Data Collection Sub-Study (for a subset): Additional 60-90 minutes interview

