C. If genetic/genomic analyses are planned, address whether the data will be contributed to a GWAS or other large dataset. Address returning unanticipated incidental genetic findings to study participants.

N/A

D. If clinical or laboratory work will be performed at JHU/JHH, provide the JH Biosafety Registration Number.

N/A

E. If you will perform investigational or standard diagnostic laboratory tests using human samples or data, clarify whether the tests are validated and/or the lab is certified (for example is CLIA certified in the U.S.). Explain the failure rate and under what circumstances you will repeat a test. For all human testing (biomedical, psychological, educational, etc.), clarify your plans for reporting test results to participants and/or to their families or clinicians. Address returning unanticipated incidental findings to study participants.

N/A

F. If your study involves medical, pharmaceutical or other therapeutic intervention, provide the following information:

Answers for this section apply only to Aim 1. Aim 3 does not involve an intervention.

a. Will the study staff be blind to participant intervention status?

Yes.

b. Will participants receive standard care or have current therapy stopped?

All participants will receive standard of care, which is case management visits and referrals to care. Participants may still receive this care post study.

c. Will you use a placebo or non-treatment group, and is that justifiable?

We will use a control group who will receive case management and will be referred to mental health care—the standard protocol for the existing Apache system.

d. Explain when you may remove a participant from the study.

Participants will be removed from the study if they move off reservation or are relocated for treatment.

e. What happens to participants on study intervention when the study ends?

The interventions are intended to be brief (2-4 hours). During the intervention and case management visits youth will become acquainted with available local resources, including visits by CMHVs.

f. Describe the process for referring participants to care outside the study, if needed.

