In cases where participants score in the high-risk category on the Opioid Risk Tool, the local research staff will consult with the two Co-PIs to determine if the participant can continue in the parent study. The parent study is an effectiveness trial, where participants can receive other services as necessary. The main factor for deciding whether they can continue in the trial is whether participating in our study is interfering with them participating in needed opioid treatment (i.e., participation in our trial may be a barrier to the time commitment needed for substance use treatment) or vice versa—i.e., participation substance abuse treatment may be a barrier to the time commitment needed to participate in our trial.

D. Reporting Unanticipated Problems/Adverse Events (AE's) to the IRB (all studies must complete this section):

Aim 1 & 3: Describe your plan for reporting to the IRB and (if applicable) to the sponsor. Include your plan for government-mandated reporting of abuse or illegal activity.

The Research Program staff will immediately alert the Local Project Director and PIs in the event of an adverse event or unanticipated problem. The PIs, Drs. [name] and [name], and the Clinical Research Supervisor, [name], will report serious adverse events to the JHSPH IRB if it is unanticipated, poses risk of harm to participants or others, and is related to the study. If there is any suspected harm to self, others, or abuse reported during an interview (including those related to opioid use), the Research Program staff will immediately report this information to the PIs. The PIs and the Local Project Director will report this to appropriate Tribal or Law Enforcement Authorities. With experience from previous studies with the White Mountain Apache community, the study team is knowledgeable of how to report this type of event without revealing study participation.

NOTE: The IRB does not require submission for all AEs, only those that are **unanticipated, pose risk of harm to participants or others, and are related to the study.**

E. Other IRBs/Ethics Review Boards:

If other IRBs will review the research, provide the name and contact information for each IRB/ethics review board and its Federal Wide Assurance, if it has one (available on OHRP's website at <http://www.hhs.gov/ohrp/assurances>).

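### Removal on moving or relocation for treatment is not reconciled with the phone-assessment provision, so SIQ collection may stop after an event that may be related to suicidality

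*Combined protocol and SAP*

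**What the plan says.** Two provisions cover overlapping people.

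- **Removal (Section V.C.5.F, item d).** "Participants will be removed from the study if they move off reservation or are relocated for treatment". The wording is mandatory. It does not say whether removal is from the intervention, from assessment, or from both.
- **Phone assessment (Section V.C.1, after CM4 and CM5).** "If necessary, assessments may be conducted over the phone for participants who start in the study but are located elsewhere during an assessment timepoint". The wording is permissive. The same paragraph expects every youth to complete CM5 at six months.

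Other sections bear on the point:

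- The primary outcome is the SIQ/SIQ-JR, scheduled at CM1 to CM5 (Section V.C.4 and Table 2).
- Eligibility text ties inpatient care to suicide events. Section IV.A accepts "release from inpatient care related to suicide ideation or attempt within past 30 days", and Section V.B.1.c says that those who have "been sent to in-patient care will continue to be eligible to enroll in this study for 30 days after their return from treatment".
- Section IV.B excludes at baseline anyone with an "unstable and severe medical, psychiatric or drug use problem that necessitates inpatient treatment".
- For high opioid risk, Section X.C.4 says: "The parent study is an effectiveness trial, where participants can receive other services as necessary". It bases continuation mainly on whether trial participation and treatment interfere with each other. Section X.C.1 also allows discontinuation when immediate opioid treatment is needed.
- Section V.C.4 says that mixed models cope well with missing data. It names no missing-data assumption and does not mention removed participants.

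**The concern.** Relocation for treatment is the part that matters most. It happens after randomisation, and in this population it may follow worsening suicidality. If staff apply the removal rule as written, the SIQ stops at that point. Surveillance of suicide events continues for all youth, but it does not supply SIQ scores.

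Two things are at stake. The first is precision, because every avoidable removal loses primary-outcome data. The second is possible bias. A likelihood-based mixed model handles removal that recorded SIQ scores explain. It does not fully handle deterioration between visits that leads to removal before the next score. If such removals differ by arm, the comparison can shift.

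Equal removal across arms cannot be taken for granted. New Hope is meant to help participants start and stay in treatment (Section V.C.1), which could raise treatment relocation in one arm. If it also lowers ideation, it could reduce relocation. The direction is therefore unknown.

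**Working it through.** **Step 1: compare the rules.** Someone sent away for treatment between CM2 and CM3 meets the removal rule. The same person is also a participant who started in the study and is elsewhere when CM3 falls due, so the phone provision covers them too. No section ranks the two rules, separates temporary absence from a permanent move, or limits removal to intervention delivery. Loss of the SIQ is possible, not certain.

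**Step 2: compare with the rest of the protocol.** Pausing participation when inpatient need arises later is consistent with the baseline exclusion in Section IV.B. What is missing is a provision for outcome collection or return. Section X.C.4 has an interference test for high opioid risk, and the removal rule has none for relocation.

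**Step 3: what can be sized.** The plan gives no removal rate, SIQ standard deviation or arm difference, so it has no figure to reproduce here. What follows is an illustration.

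Inputs:
- Correlation r between visits, exchangeable: 0.2 (planning value in Section III.B) to 0.7 (assumed). Higher values are plausible because SIQ recall covers six months and the windows overlap.
- Difference in removal between first-stage arms: 5 to 10 percentage points (assumed).
- Gap: removed participants score 0.5 to 1.0 SD worse at the first missed visit (assumed).
- k recorded visits before removal, 1 to 4. Removal is driven by the first unrecorded score (assumed, and the unfavourable case).

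Formulas:
- Share of the gap recovered from recorded scores: R² = k·r² / (1 + (k−1)·r).
- Shift at the first missed visit: removal difference × gap × (1 − R²).
- Shift at each later visit: removal difference × gap × (r − R²), if the gap fades as the correlation implies.
- Average over the four visits CM2 to CM5, with zero for visits recorded before removal.

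Upper end, k = 1, difference 0.10, gap 1.0:

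| r | R² | First missed visit | Each later visit | Average CM2–CM5 |
|---|---|---|---|---|
| 0.2 | 0.04 | 0.096 | 0.016 | (0.096 + 3×0.016)/4 = 0.036 |
| 0.5 | 0.25 | 0.075 | 0.025 | (0.075 + 3×0.025)/4 = 0.0375 |
| 0.7 | 0.49 | 0.051 | 0.021 | (0.051 + 3×0.021)/4 = 0.0285 |

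The maximum is 0.039 SD, near r = 0.38.

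Lower end, k = 4, r = 0.7, difference 0.05, gap 0.5: R² = 4×0.49/(1 + 3×0.7) = 0.632. The shift at CM5 is 0.05 × 0.5 × 0.368 = 0.0092, and the average is 0.0092/4 = 0.0023 SD.

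**Step 4: check.** A simulation with 1,000,000 participants per arm, regressing on recorded visits, gave average shifts of about 0.036 SD (15% versus 5% removed, gap 1.0, r = 0.2, k = 1) and about 0.002 SD (10% versus 5%, gap 0.5, r = 0.7, k = 4). The shift was zero to within simulation error when removal was driven by the last recorded score, and again when 10% were removed in both arms with the same gap.

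**The case against.** The strongest defence is that the two texts can be read together: permanent moves fall under the removal rule, and absence at a timepoint falls under the phone rule. The removal line is a short answer to an ethics-form prompt, and operational detail may sit in the policies and procedures manual, which is not among the documents. That reading is workable, but the protocol does not state it, and relocation for treatment is named expressly as a ground for removal.

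Several further points stand:

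- The treatment in the removal rule is unspecified and may be medical or for substance use. The sections linking inpatient care to suicide events concern eligibility, not events after randomisation. Moving off reservation has no documented link to SIQ.
- All arms receive the same case management visits, SIQ scoring and referral. Differential removal is an assumption.
- Because SIQ is scored at each visit and drives referral (Sections V.C.1 and X.C.1), recorded scores may explain many removals, and the mixed model then handles them.
- The contrast with Section X.C.4 is limited, since Section X.C.1 also allows treatment-related discontinuation.
- The current risk response relies on local staff and services, so caution about remote follow-up of suicidal youth has a safety rationale.

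A reader might also infer a sample-size shortfall from the attrition allowance ("Adjusting these estimates for 30% attrition"). How that allowance was calculated is a separate question, and it does not measure harm from the removal rule.

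**Conclusion.** The point holds as an unresolved rule about collecting the primary outcome, and it should be fixed. Followed as written, the removal rule stops SIQ collection after an event that may be related to suicidality. The loss of precision applies to every avoidable removal. Bias is conditional: it needs removal that depends on unrecorded SIQ and that differs by arm.

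Under the assumed inputs the shift averages about 0.002 to 0.04 SD over CM2 to CM5. It is zero if recorded scores explain removal, or if both removal rate and gap are equal across arms. The range also assumes that the gap fades. If it persisted at every later visit, the average could reach the first-missed-visit value in the table.

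A reader might go further and conclude that the plan certainly discards SIQ data after relocation, or that the primary comparison is biased for or against New Hope. The documents support neither. The phone provision may govern in practice, and no relocation rate or arm difference is given, so neither the size nor the direction of any bias can be established.

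**What to change.** Amend Section V.C.5.F, item d, as follows:

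1. Moving off reservation or relocation for treatment ends in-person visits and intervention delivery only.
2. SIQ is attempted by phone, under the existing provision in Section V.C.1, at each remaining timepoint through CM5. The exceptions are withdrawal of consent and contact that would interfere with treatment, which is the test Section X.C.4 already uses.
3. The SIQ risk response in Section X.C.1 is adapted for remote contact.
4. Participants who return resume assessments at the next timepoint.
5. All participants stay in the group or groups to which they were randomised.
6. Removals and their reasons are reported by arm.

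A sensitivity analysis that assumes worse SIQ scores after relocation for treatment than the model predicts, with values set in advance, would be useful but is optional.

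The cost is a protocol amendment with ethics review, a remote version of the risk response, and up to four phone assessments (CM2 to CM5) per relocated participant by existing staff. The protocol already accepts phone assessment in principle.
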